Cover page:

Title: Investigation of TEST (Transcranial Electric Stimulation Therapy) for Chronic Pain

NCT05113563

IRB approval date: March 26, 2024.

Lay Summary of Proposed Research

This section is intended to provide a basic overview of the study including a description of its purpose, study procedures, and subject population. The summary should provide a concise overview of the study for non-scientific and scientific members of the IRB. Please avoid medical or technical terminology. In general, the abstract of a grant does not provide a suitable lay summary.

About 30% of American adults experience daily chronic pain, which is defined as pain persisting 3 months or more past the expected time of healing that does not resolve with treatment. In addition to considerable suffering, chronic pain is associated with mental illness (including depression, anxiety) and the risk of substance use disorders. Non-opioid medications are recommended but are often don't provide a full response. As a result, opioids are sometimes prescribed, which has the risk of misuse or addiction. Alternatively, patients may resort to other substances of abuse (such as alcohol or cannabis).

Our goal in this study is to investigate TEST (Transcranial Electric Stimulation Therapy) for chronic pain. TEST is similar to electroconvulsive therapy (ECT) in that an electrical stimulus is delivered to the brain. However, the dose of stimulation used for TEST is lower than ECT, and we expect that a seizure will not be generated with TEST (although general anesthesia is required). A previous publication has shown that TEST is effective for treatment resistant depression, without effects on memory that can accompany ECT.

We propose to investigate the feasibility of TEST in subjects with chronic pain. This will be an open-label study where subjects (n=12) are administered 8-10 sessions of TEST over 4 weeks. Measurements of pain, mood, and memory will be obtained before and after the sessions. Our hypothesis is that TEST will be feasible in this subject population and pain symptoms will improve.

Background, Significance, and Rationale

In this section, provide a brief summary of the status quo of the relevant work field and how the proposed study will advance knowledge. Specifically, identify the gaps in knowledge that your project is intended to fill. If no gaps exist that are obviously and directly related to your project, explain how your proposed research will contribute to the overall understanding of your field. Describe potential impacts of your project within your field of study and in a broader context. Provide a critical evaluation of existing knowledge. The literature review does not have to be exhaustive.

Chronic pain non-cancer pain (CNCP) can be difficult to treat, although it affects up to 30% of adults in the United States. While there are non-opioid alternatives for CNCP, such as antidepressants and anticonvulsants, many patients experience only a partial response. For example, with anti-depressant treatment about one in three patients with neuropathic pain will experience a moderate effect on pain relief (Sarto et al, 2010). Anti-epileptic therapies for chronic pain are associated with a high incidence of side effects (Wiffens et al, 2013). Thus, novel treatment approaches are needed for chronic pain.

Protocol Summary Form

Electroconvulsive Therapy (ECT) has been in use for decades. The main indications for ECT are treatment resistant depression and refractory catatonia. For these disorders, the efficacy is close to 50-90%. In the past, ECT was used for chronic pain and studies from the 1950s and 1960s reported that ECT alleviated this condition. However, these studies are limited to case reports and studies lacking an appropriate control group. The largest and most recent case series included 21 patients with primary chronic pain who had been refractory to pain treatment (Bloomstein et al, 1996). The patients were treated with ECT (between 5 and 14 treatments). In nine of the 21 patients, the pain syndrome preceded the onset of depression, in another nine patients the pain onset either coincided with or came after the depression, and in three patients the sequence of pain and depression was indeterminate. Of the 21 patients, 19 reported a significant improvement in pain, while one participant experienced no change and one was removed from the study due to medical complications unrelated to ECT (Bloomstein et al, 1996). To our knowledge, the remainder of the literature on ECT for chronic pain is limited to case reports of < 5 patients and range from 1953 to 2020, with no systematic investigation of ECT for this condition. However, these case reports report that ECT was efficacious in reducing chronic pain.

TEST is a form of brain stimulation that resembles ECT, except that the dose is approximately 1/8th the dose delivered in ECT. A recent study showed that TEST is helpful for treatment resistant unipolar and bipolar depression (Regenold et al, 2015; please note that TEST was referred to as 'NET' in this publication). This proof-of-concept trial enrolled 11 subjects who received open label treatment with TEST. The mean Hamilton Depression Rating Scale (HDRS) scores declined significantly with TEST, from 20.3 to 8.6 ($p = 0.001$). Response and remission rates were 73% and 55%. Cognitive testing was done using the Mini-Mental State Exam and the Autobiographical Memory Inventory-Short Form. The results showed that memory was not affected by TEST. In this publication, TEST was delivered at 1/8th the usual ECT dose for 7 seconds. Please note that a sister study is currently being performed at NIMH (in collaboration with our group here at NYSPI) by [name] using these same parameters. This protocol will use the same parameters as those used by Regenold et al (2015), as delineated in the procedures section.

The goal of this study is to investigate TEST for chronic pain. Like ECT, TEST will provide widespread stimulation of the prefrontal cortex, including the medial prefrontal cortex (mPFC) and the anterior cingulate (ACC) (Blumenfeld et al 2003 and Lee et al 2016). Imaging studies show that the emotional and cognitive perception of pain are modulated by these brain regions. Using a meta-analytic, data-driven approach, two studies have shown that the ACC and mPFC regulate pain processing (de la Vega et al 2016 and Lieberman et al 2015). Thus, we will investigate whether the stimulation of these brain regions with TEST has an impact on chronic pain.

This is a preliminary, open label feasibility study in adults with CNCP. Subjects will be recruited from the pain clinics of Columbia University Irving Medical Center. Given that this is a feasibility study, it is open to participants with chronic pain caused by a wide range of disorders. Please note that chronic pain, independent of the original etiology, has been shown to involve the medial prefrontal cortex and cingulate. Thus, in this pilot study, the procedure is open to patients with different primary causes of pain who suffer with chronic pain. Subjects will be admitted to the research unit at NYSPI. They will receive three treatments weekly for a total of 8-9 treatments, using the dosing from the previous study of refractory depression (Regenold et al, 2015). Ratings of pain, mood, and memory will be obtained before and after the TEST sessions, and weekly for 4 weeks after the end of the TEST sessions.

Specific Aims and Hypotheses

Concisely state the objectives of the study and the hypothesis or primary research question(s) being examined. There should be one hypothesis for every major study procedure or intervention. For pilot studies, it is important not to overstate the study's objectives. If there are no study hypotheses, describe broad study goals/aims.

Specific Aim 1: We will determine the feasibility of administering NET to participants with chronic pain. Like ECT, NET will be delivered three days a week for three weeks (for a total of 8 to 9 sessions). We will recruit 6 subjects with a diagnosis of chronic pain, defined as pain lasting more than 6 months, that has not remitted with pharmacotherapy, with no other known treatment (examples include chronic postoperative pain, low back pain, musculoskeletal pain, fibromyalgia, visceral pain and neuropathic pain, including complex regional pain syndrome). Our hypothesis is that NET will prove to be safe and tolerable in this patient population and will show preliminary efficacy, defined a priori as a decrease in pain of at least 30%.

Specific Aim 2: We will determine the preliminary efficacy in 6 patients with chronic pain (using the same criteria as above) who have comorbid major depression. We will use the same inclusion criteria and the same outcome measures as Aim 1, obtained before and after the NET sessions. Our hypothesis is that NET will be safe, tolerable, and will have preliminary efficacy on symptoms of major depression in addition to chronic pain (improvement of at least 30%).

Specific Aim 3: We will develop the most appropriate anesthesia regimen for NET. In the past, NET has been delivered using the same anesthesia regimen as ECT. However, since no seizure is elicited with NET, the patient is likely to require only brief sedation rather than general anesthesia for the procedure (as is standard for ECT). Whereas it is typical during ECT to adjust the administered dose of anesthetic medications in subsequent treatments to minimize the time requiring ventilatory/circulatory support and post-ictal confusion, we will determine optimal dosing strategies for NET. We hypothesize that NET participants will require only minimal sedation without neuromuscular blockade.

Description of Subject Population

In this section, you are to describe each subject population of the study. The demographics of the population should reflect the gender and ethnic distribution of each population being studied. Enter each subject population's sample size, Gender, Racial, and Ethnic breakdown, and finally, describe each subject population.

Participants with Chronic Pain

Subject Population	Number of completers required to accomplish study aims	Projected number of subjects who will be enrolled to obtain required number of completers	Age range of subject population
Chronic pain patients	12	20	22-60

Gender, Racial, and Ethnic Breakdown:

We expect to enroll 50% women; 50% white, 25% black; 25% Hispanic/Latino

Description of subject population: Participants with refractory chronic pain with at least 3 months duration with a diagnosis of chronic postoperative pain, low back pain, musculoskeletal pain, fibromyalgia, visceral pain or neuropathic pain, including complex regional pain syndrome

Suicide Risk Management Plan

This section will include all information regarding the Suicide Risk Management Plan.

This study involves no delay to treatment, no medication taper, all participants receive active treatment. Participants are asked to not change their medication while admitted to the research unit. They can change medications during the follow-up phase. The Columbia Suicide Severity Rating Scale (CSSRS) will be used at screening, administered by a study physician. Any participant reporting suicidal ideation or behavior (defined as any answer of 'yes' to questions 1, 2 or 6 on CSSRS) to any member of the research team will be evaluated by Drs. [name], [name], or [name]. If the patient is an active suicide risk, 911 will be called and/or the participant will be escorted to the Emergency Department. If the participant is not an active risk, they will be provided with referrals for outpatient treatment. If the participant has outpatient treatment in place, their clinician will be notified. [name], [name], or [name] will follow up with the participant until their clinical care is in place.

The C-SSRS is done at screening. After this, the Beck Depression Inventory (BDI) is acquired during the inpatient stay and during the follow up period. The BDI is a self-report measure. The BDI will be used to assess risk and any of the following criteria will trigger a clinical assessment by a psychiatrist regarding suicide risk: 1) an answer of "yes" to question 9 (thoughts of killing self); 2) a score higher than 16; 3) an increase in BDI score of 10 points or more from the baseline BDI (obtained on scan day) even if the total score remains below 16. Please note that the follow up assessments include a phone call with a study psychiatrist. As mentioned above, the psychiatrists are Drs. [name], [name], or [name]. Participants will be advised that they can call the lab to speak with a psychiatrist when the link is sent. A research assistant will check the responses on the day that they are sent to check the responses.

Recruitment Procedures

This section will include all information regarding your study's recruitment process/procedures.

Describe settings where recruitment will occur. Participants will be recruited using advertisements from Facebook and Craig's list (not limited to NYC)

How and by whom will subjects be approached and/or recruited? N/A

How will the study be advertised/publicized? Facebook and Craigslist

Attach any ads/recruitment materials requiring review at this time in the Uploads section.

Clinical Trials:

Does this study involve a clinical trial? No Yes

Please provide the NCT Registration Number for your Clinical Trial. NCT05113563

YOU MUST REGISTER AT ClinicalTrials.gov IMMEDIATELY UPON RECEIPT OF IRB APPROVAL AND PRIOR TO ENROLLMENT OF THE FIRST SUBJECT. YOU WILL BE PROVIDED WITH A NCT REGISTRATION NUMBER ON REGISTRATION. PLEASE REVISE THIS SECTION OF THE PROTOCOL SUMMARY FORM TO INCLUDE THE NCT NUMBER AND RE-SUBMIT AS AN AMENDMENT TO THE IRB.

Concurrent Research Studies

In this section, please identify if subjects in this study participate in or will be recruited from other studies.

Describe where subjects are recruited from. N/A

Describe the recruitment source for (Must provide IRB Number, PI and Title). N/A

Inclusion/Exclusion Criteria

This section details your study sample(s) and addresses the requirement for risk minimization. You may choose to divide your sample by population (healthy controls vs. patient population) or by procedure (subjects who will have an MRI vs. those who will not) and then define different sets of criteria for each.

For each sample, create or insert a table to describe detailed criteria for study inclusion and exclusion and the method you will use to ascertain each criterion. The method of ascertainment may describe tests, scales and instruments. When relevant, indicate the level of training of the person who will make the assessment (e.g. clinical interview by a psychiatrist).

Inclusion/Exclusion Criteria need to be numbered and listed in outline form (see Table template below).

See record

Consent Procedures

Explain, in this section, the procedures for obtaining consent from study participants.

If the eligibility screening for this study is conducted under a different IRB protocol, enter the NYSPI IRB# N/A

Waiver of Consent / Authorization

The following sections are to be completed for the appropriate waiver/alteration of consent.

Waiver of Consent for use of Protected Health Information (PHI)

What records do you wish to review? N/A

What information are you seeking access to? N/A

Describe your plan to protect identifiers from improper use and disclosure. N/A

Describe your plan to destroy the identifiers as soon as possible, consistent with the conduct of the research, or provide a health or research justification for retaining the identifiers or explain how retention is required by law. N/A

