- b) Clinical Global Impression (CGI) scale, a measure of symptom severity, treatment response and the efficacy of treatments as measured by a study physician (three days week).
- c) Beck Depression Inventory (BDI): the 21 item self-report rating scale for depression (weekly).
- d) Beck Anxiety Inventory (BAI): the 21 item self-report rating scale for anxiety (weekly).
- e) The Defense and Veterans Pain Rating Scale (DVPRS), a graphic tool that clinicians use to facilitate self-reported pain from patients, including the supplemental questions (weekly).

Subjects will be asked to confirm that they have had no food or drink for 8 hours with the exception of required prescription medication which they can take by mouth on the morning of the procedure with a small sip of water. They will then be asked to change into a hospital gown, escorted to the ECT suite. Vital signs (blood pressure, heart rate, and oxygen saturation) will be recorded at baseline and every 5 minutes through the end of the procedure. EEG leads will be placed in the middle of the forehead and on the left mastoid to monitor for any seizure activity. The EEG output will be reviewed to assess the absence of a seizure.

General anesthesia will be performed by an anesthesiologist. TEST will be sub-convulsive, but since seizure threshold determination for ECT involves sub-convulsive stimulation and is done routinely, there are no substantial differences or additional risks with TEST.

Protocol Summary Form

The absence of a seizure will be verified per usual ECT protocol by observing for tonic-clonic movements in a lower extremity isolated from neuromuscular blockade by a blood pressure cuff maintained above systolic blood pressure and with interpretation of the electroencephalogram (EEG) generated from the electrodes placed in the center of the forehead and one each on the left and right mastoid processes.

In the event that a subject has a seizure, the TEST dose will be lowered to 1/10th of the ECT dose (from 1/8th). The seizure will be discussed with the participant, including the plan to reduce the dose. If a participant has a seizure at 1/10th dose, they will be discontinued from the study.

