Subjects will be monitored until they recover. The subjects' oxygen saturation, BP and heart rate must be back at baseline before discharge (oxygen saturation >95%, BP and HR within normal limits and within +/- 10 mmHg or BPM). The expected recovery time is 60 to 80 minutes. Subjects will remain in the recovery area until they are assessed by the physicians and ready to leave the ECT suite. Subjects will return to the inpatient unit after each TEST session when they are awake from anesthesia and have stable vital signs.

At the end of the TEST sessions, subjects will be asked to complete the following assessments prior to discharge from the unit:

- a) The Hamilton Depression Rating Scale (HDRS): the 24 item assessment scale regarding symptoms of depression.
- b) The Brief Pain Inventory (BPI): a self-administered questionnaire (0- 10, developed to quantify measures of pain
- c) The Defense and Veterans Pain Rating Scale (DVPRS), a graphic tool that clinicians use to facilitate self-reported pain from patients, including the supplemental questions.
- d) Columbia Autobiographical Memory Interview – short form (AMI-SF), which is used to assess memory changes in studies of ECT.
- e) Trail Making Test (TMT), Parts A and B, to assess executive function.
- f) The Stroop Color Word Test to also assess executive function.
- g) Repeatable Battery for the Assessment of Neuropsychological Status, which is a brief, individually administered battery to measure cognitive decline or improvement across five domains: immediate memory, visuospatial skills, language, attention, and delayed memory.
- h) Beck Depression Inventory (BDI): the 21 item self-report rating scale for depression
- i) Beck Anxiety Inventory (BAI): the 21 item self-report rating scale for anxiety
- j) The Patient-Reported Outcomes Measurement Information System (PROMIS)-29, which assesses pain interference and quality of life.
- k) McGill Pain Questionnaire a self-reported measure of pain studied with a number of diagnoses, and it assesses both the quality and intensity of pain.
- l) Clinical Global Impression (CGI) scale, a measure of symptom severity, treatment response and the efficacy of treatments as measured by a study physician.
- m) Montreal Cognitive Assessment (MoCA) test: a brief, simple screening for cognitive impairment.

Protocol Summary Form

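### As written, Aim 3's hypothesis of minimal sedation without neuromuscular blockade cannot be tested: no such session is described and no anaesthesia outcome is listed

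*Combined protocol and SAP*

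**What the plan says.** Specific Aim 3, under Specific Aims and Hypotheses, sets out to develop an anaesthesia regimen suited to the treatment. It reasons that, because no seizure is elicited, "the patient is likely to require only brief sedation rather than general anesthesia for the procedure". After noting that ECT practice adjusts anaesthetic doses from one treatment to the next, it adds that "we will determine optimal dosing strategies for NET". The hypothesis follows: "We hypothesize that NET participants will require only minimal sedation without neuromuscular blockade".

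Other sections read differently:

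- The Lay Summary describes the stimulation as milder than ECT, "although general anesthesia is required".
- The procedures narrative says "General anesthesia will be performed by an anesthesiologist", with no exception. It verifies the absence of a seizure by "observing for tonic-clonic movements in a lower extremity isolated from neuromuscular blockade by a blood pressure cuff". Participants go back to the unit "after each TEST session when they are awake from anesthesia".
- Risks/Discomforts/Inconveniences names glycopyrrolate, methohexital and succinylcholine as anaesthesia drugs. It attributes one risk partly to neuromuscular blockade and speaks of a short-lived need for ventilatory support.

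On measurement, the procedures narrative says "Vital signs (blood pressure, heart rate, and oxygen saturation) will be recorded at baseline and every 5 minutes", and EEG is used to look for seizure activity. Analysis and Outcomes names four outcome measures: willingness to take part, tolerability, cognition and pain.

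**The concern.** A hypothesis that something is not required needs observations with that thing withheld, a measure of how those sessions went, and a rule for judging success. The protocol appears to supply none of the three for Aim 3.

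Two consequences follow. First, a final report that sedation alone is enough would have no data behind it. Secondly, if the anaesthetist does in fact adjust doses between sessions, nothing in the plan would let a reader see what was given at each session or how one strategy came to be called optimal.

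**Working it through.** The documents give no figure, threshold or sample-size argument for Aim 3, so there is no stated number to reproduce. The check sets the sections side by side and counts what is planned.

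**1. What each section says about the condition under study**

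| Place | General anaesthesia | Neuromuscular blockade | Session without them described? |
|---|---|---|---|
| Specific Aim 3 | Expected to be unnecessary | Hypothesised to be unnecessary | No; intent only |
| Lay Summary | Required | Not mentioned | No |
| Procedures narrative | Given, no exception | Presupposed by the isolated-limb check | No |
| Risks, drug list | Three agents named | Succinylcholine is one of them | No |
| Risks, numbered list | Referred to, with ventilatory support | Named as a source of risk | No |

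**2. Sessions available.** There are 12 participants. The background and Aim 1 give 8 to 9 sessions each; the Lay Summary gives 8 to 10.

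- 12 × 8 = 96
- 12 × 9 = 108
- 12 × 10 = 120

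None of these 96 to 120 sessions is described as given without general anaesthesia and blockade. As written, the number of observations under the hypothesised condition is 0.

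**3. Planned measures of anaesthetic need**

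- Analysis and Outcomes: 0 of 4 outcomes. Tolerability is listed but is not tied to anaesthetic need.
- Assessment Instruments, items a to o: 0 of 15.
- Lettered schedules in the procedures: screening 12 + baseline 6 + inpatient 5 + discharge 13 = 36; 0 of 36.
- Recorded within a session: three vital signs, plus EEG. Agents, doses, depth of sedation and ventilatory-support time are not mentioned.
- Recovery: an expected 60 to 80 minutes and vital-sign conditions for leaving. The actual time to recovery is not stated to be recorded or analysed.

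**4. Adjustment rule and criterion.** Where the protocol intends a treatment change, it writes a rule: the stimulus dose is reduced after a seizure. No comparable rule exists for anaesthesia. Aims 1 and 2 carry a 30% improvement threshold; Aim 3 carries no criterion.

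**5. What 12 participants could show if the condition were studied (illustration only).** Assume a yes/no result per participant: manageable or not under the hypothesised regimen. This endpoint is not in the documents. With no failures among n participants, the exact one-sided 95% upper bound on the failure rate is 1 − 0.05^(1/n).

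- n = 12: 1 − 0.05^(1/12) = 22.1%
- n = 6: 1 − 0.05^(1/6) = 39.3%

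Even a clean result would therefore be imprecise. With 0 informative observations, no bound can be computed at all.

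**The case against.** The strongest reply is that Aim 3 is developmental. It points to the ECT habit of changing anaesthetic doses over successive treatments so as to shorten ventilatory and circulatory support and limit confusion afterwards, and then promises to work out strategies for this treatment. That names a possible mechanism and possible targets. On this reading blockade need not be fixed at every session. The drug list sits in the risk section, and the isolated-limb check is described as usual ECT practice. The flat contrary statements concern general anaesthesia more directly than blockade.

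Part of this stands. Between-session adjustment is a fair reading of the intent. It is never turned into a procedure, a record or a criterion, though, and adjusting doses within general anaesthesia with blockade would not show that blockade can be omitted.

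The counts can also be challenged, and fairly. The 15-item instrument list omits the McGill Pain Questionnaire and the Mini-Mental Status Exam, both of which are scheduled, so it is not exhaustive. The 36 schedule entries are mostly questionnaires and cognitive tests and largely repeat those instruments. Procedure-day anaesthesia data would not naturally appear there. The counts are supporting evidence only.

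The vital signs and recovery conditions do bear on recovery and support. They are monitoring rather than a defined Aim 3 endpoint, and they come only from the regimen actually given. Lastly, a part of the public document just before the procedures narrative was not available. The visible account of a session nevertheless runs from fasting to recovery and states general anaesthesia without qualification.

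**Conclusion.** The concern holds. Aim 3 states a hypothesis about a condition that the described procedures never produce, and it has no outcome or decision criterion. This is more than missing detail: a team that followed the text exactly would finish with nothing that bears on the hypothesis.

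The damage is confined to one of three aims and does not reach the feasibility or pain outcomes. The conclusion rests on the visible text being the operative account of a session, and on blockade being used wherever the isolated-limb check is used. It is a change that should be made, not one that threatens the study as a whole.

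**What to change.** The study team should first reconcile Specific Aim 3 with the Lay Summary, the procedures narrative and the risk section. Which regimen is right is a clinical matter on which no position is taken here. Then one of two routes applies.

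- **If the procedures stand as written:** remove the hypothesis about minimal sedation without blockade. Restate Aim 3 as descriptive, tabulating by session number the agents and doses given, ventilatory-support time and recovery time. Draw no conclusion about sedation alone.
- **If anaesthesia is meant to vary:** align the procedures with the aim, report what was given at each session, and state in advance what result would count as supporting the hypothesis. The plan should also acknowledge how little precision 12 participants give.

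On either route, add the Aim 3 measure to Analysis and Outcomes.

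The cost is small: rewording one aim, adding one line to the outcomes and, because the documents do not say these items are recorded, probably a short per-session form. The second route also means editing the procedures. At least three participants had already completed when this version was written, so the plan should say whether their anaesthesia details can be recovered from clinical records. Under the first route the price is a more modest Aim 3.
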